1.1 Rationale

Excess adiposity and reduced lean body mass has been linked to reduced survival and quality of life in women with advanced breast cancer (ABC). Preclinical models have shown that energy restriction and weight control protect normal cells from the effects of chemotherapy whilst increasing the sensitivity of malignant cells to oxidative stress, apoptosis and DNA damage – the so-called 'differential stress response'. Whilst patients with reduced lean body mass have increased chemotherapy toxicity and poorer outcome. The B-AHEAD 3 trial will randomise women initiating first, second or third line treatment for ABC to energy restriction and resistance exercise vs normal diet and resistance exercise. B-AHEAD 3 will test whether an energy restricted diet adds to the antitumour effect and ameliorates toxicity of chemotherapy compared to an exercise only intervention in the clinical setting.

2. Background

2.1 Weight loss, energy restriction and outcome amongst patients with ABC

Being overweight or gaining weight during treatment increases relapse and reduces survival in women with early breast cancer (1, 2), whilst weight loss / energy restriction may improve survival (3). Excess weight has also been linked to a poorer survival amongst patients with ABC, in some (4) (5-7), although not all studies (8), and to reduced quality of life (9). In a previous study of serial measures of weight, adiposity and energy balance amongst ABC patients receiving chemotherapy we demonstrated potentially detrimental gains in adiposity associated with increased energy intake during chemotherapy (10).

In animal models, energy restriction reduces both tumour growth and tumour progression (11, 12) (13). This reduction is mediated by well characterised metabolic and signalling changes which occur during energy restriction affecting both the tumour cells and tumour stroma (reviewed in Ford et al 2013 (14)). Energy restriction reduces serum concentrations of multiple host factors including insulin, insulin-like growth factor-1, leptin, steroid hormones, cytokines, vascular regulators, inflammatory mediators and increases adiponectin. In addition reductions are also seen in cellular and structural components of the tumour microenvironment, including hypoxia inducible factor-1 (HIF-1) (15), haem oxygenase-1 (HO-1), vascular endothelial growth factor (VEGF), inducible nitric oxide synthase (iNOS), and reductive oxygen species and hydrogen peroxide (16). These secreted and structural host factors are extrinsic to, but interact with, the intrinsic molecular characteristics of breast cancer cells (including breast cancer stem cells). A recent animal study reported that energy restriction reduced epithelial-tomesenchymal transition and reduced tumour progression in aggressive murine claudin-low and basallike mammary tumour models (17). Similarly energy restriction reduced the metastatic potential of triple-negative breast cancer by down regulating the production of extra cellular matrix and metastasis associated proteins (18). These studies suggest that the benefits of energy restriction are likely to be realised across the different histological subtypes of breast cancer (12) (18) (19).

2.2 Possible mechanisms mediating the link between weight, energy restriction and outcome amongst patients with ABC

The adverse effects of excess weight and weight gain on prognosis in breast cancer patients are thought to be largely mediated by reduced insulin sensitivity, impaired glucose tolerance and hyperinsulinemia (20). Reduced insulin sensitivity and impaired glucose tolerance have been reported in 50% of patients with metastatic breast cancer (MBC) in two recent cohorts where it was linked to poorer response (7) (21). In women receiving paclitaxel chemotherapy for MBC, Stebbing et al reported clinical benefit rates of 40.5% vs 65.8% in women with and without impaired glucose tolerance respectively (7). In a multivariate analysis the odds ratio (OR) of disease progression per unit increase in fasting glucose was 5.47 (95% CI 2.05–14.60). Similarly, Gennari et al reported a median progression free survival (PFS) of 8 months (IQR 2-17) in MBC patients with insulin resitance (HOMA index >2.5) compared with 14 months (IQR 8-18) in patients with normal insulin sensitivity (HOMA index <2.5) (n = 87 standard). The multivariate hazard ratio of disease progression was 2.28 (95% CI 1.06–4.89) in patients with insulin resistance (21). Insulin resistance is common amongst these patients and can be further increased during chemotherapy because of weight gain, direct cellular effects of chemotherapy and the use of corticosteroids as anti-emetics and to prevent reactions to the taxanes (20, 22).

Energy restriction is thought to act partly down stream of insulin through inhibition of the mTOR signal transduction pathway. The likely benefits of energy restriction in patients with MBC are suggested by beneficial effects of mTOR inhibitors such as everolimus (Ev) which has been shown to improve PFS when given in combination with endocrine therapy (23, 24) and chemotherapy (23). However, drugs such as Ev are associated with a significant increase in toxicity. Our hypothesis is that weight loss and energy restriction in advanced disease will phenocopy mTOR inhibitors in extending PFS but, in contrast to pharmacological mTOR inhibition, will reduce toxicity and improve quality of life. It is also worth noting that energy restriction mimetics such as metformin are also being tested in MBC (25-27).

2.3 Weight, energy restriction and toxicity of and response to chemotherapy

Obesity may specifically reduce the efficacy of chemotherapy. Obese patients with breast cancer consistently have a poorer response to neoadjuvant chemotherapy, even with adequate dosing (28-31). Obesity leads to resistance to gemcitabine chemotherapy in an animal model of metastasis. Impaired response was linked to impaired blood flow, altered pharmacokinetics of tissue and tumour distribution and altered expression of genes related to uptake and metabolism of chemotherapeutic agents (32). Reduced response to neoadjuvant chemotherapy has recently been reported in patients with increased hepatic stearoyl co A desaturase (SCD) activity (the rate limiting enzyme of fatty acid biosynthesis), which occurs in obese insulin resistant subjects. Specifically SCD activity is increased in association with high circulating insulin and leptin, increased intake of carbohydrate and saturated fat and a low intake of n-3 fats (33).

In preclinical models, energy restriction protects normal cells from the effects of chemotherapy and radiotherapy, whilst increasing sensitivity of malignant cells via increased oxidative stress, apoptosis and DNA damage – the so-called 'differential stress response' (34-37). A recent paper reported that 2 days of fasting pre chemotherapy promoted fat oxidation and hematopoietic stem cell augmentation and stem cell regeneration and protection of lymphocytes from chemotoxicity (38). These data indicate that energy restriction may reduce chemotherapy associated toxicity and increase the effectiveness of treatment. The National Institute Health trials register Clinicaltrials.gov (USA) currently has six ongoing small scale trials of fasting and chemotherapy toxicity (two in the Netherlands, one in Germany and three in the USA), and one USA study assessing radiotherapy toxicity (39) in addition to a further eight low carbohydrate diet trials (all in the USA) amongst patients with advanced cancer patients with breast and other cancers (accessed on 13th August 2014)(40).

2.4 Rationale for testing an intermittent energy restricted diet in advanced metastatic breast cancer patients

The main aim of dietary intervention is to reduce energy intake. Our recent review of dietary intervention studies in animals (manuscript in preparation) indicates that energy restriction, mainly achieved by reduced carbohydrate intake, is associated with reduced tumour growth and progression in mice with orthotopically transplanted metastatic tumours (11, 12, 41), or with carcinogen induced mammary tumour models (42, 43).

In the trial outlined here we plan to use intermittent energy restriction (IER). Our previous studies suggest this may be the most efficacious way to achieve energy restriction. Previous randomised trials in women without breast cancer indicate that IER is associated with greater weight loss, preservation of fat free mass and reduction of insulin serum concentrations compared with standard continuous energy restriction (CER). The IER diet we have developed involves two consecutive days of severe energy restriction and five days of normal healthy eating. (44). We have initiated a second trial specifically to test this IER amongst women receiving adjuvant or neoadjuvant chemotherapy (B-AHEAD 2) for early breast cancer. Our preliminary data indicate that the IER taken for just 2 days per week is more effective for weight control during chemotherapy than standard daily dieting, since the 2 restricted days can be administered between cycles of chemotherapy (45).

Overall fat intake is reduced on IER, mainly through reducing saturated and polyunsaturated n-6 fats, whilst maintaining intake of monounsaturated fat and promoting n- 3 fats. Previous studies indicate that reducing intake of fat, mainly n-6 fats without reducing calories reduced growth and metastases of breast tumours transplanted into athymic nude mice (46) and Wistar rats (47), but not in two further studies amongst Wistar (48) and Fisher rats (49). Phase 2 studies have reported supplementation with the n- 3 fat docosahexaenoic acid (DHA, 1.8 g/day) improves the efficacy of chemotherapy amongst patients with MBC, possibly due to altered cell membrane structure and increased chemotherapy uptake and enhancement of the oxidative stress generated by anthracylines due to peroxidation of DHA (50, 51). The optimum protein intake for energy restricted women with ABC receiving chemotherapy needs careful consideration. Patients need to receive adequate protein to maintain lean body mass. Maintained lean body mass (not BMI or fat stores) is essential to limit chemotherapy toxicity. Recent studies indicate that chemotherapy toxicity is inversely related to lean body mass rather than any other measurable parameter (52). There are few data to guide optimal protein intakes to maintain lean body mass in non-cachexic cancer patients. A recent review recommends 1.2 g per kg body weight (53), which is comparable to recommendations for weight loss patients in the non-cancer setting and also the amount in the IER diet (54).

Higher protein intake maintains lean body mass as it suppresses gene expression in the ubiquitinproteasome pathway in skeletal muscles to prevent atrophy and promotes muscle protein synthesis via the mTOR signalling pathway (55). The potential for higher protein intakes, specifically branch chain amino acids to stimulate mTOR and growth of tumours in cancer patients is a potential concern. This has been shown in two animal studies in a carcinogen induced mammary tumour (56) and a human ER +ve, PR and HER -ve xenograft model (WHIM16) (57). In the latter study there was a two fold increase in tumour growth with an isocaloric diet which provided 21% compared to 7% of energy as protein linked to stimulation of the IGF/AKT/mTOR pathway and epigenetic effects (57, 57).

With the exception of these data the balance of evidence from the majority of animal and human studies indicates that higher protein intakes will not promote tumour growth amongst breast cancer patients. Reduced tumour growth and metastases with energy restriction has been achieved with maintained protein intake in the animal studies described above (11, 12, 41) (42, 43). Reduced relapse events amongst early breast cancer patients in the Women's Intervention Nutrition Study were achieved with a 10% energy restriction and a 50% reduction in fat intake and maintained protein intake (1g/kg body

weight) (OR 0.76 [95% CI = 0.60 to 0.98]) (3). Higher protein intakes are consistently linked with improved outcome amongst breast cancer patients (11, 12, 41), perhaps because they enable preservation of lean body mass. Trials of nutrition support have mainly found protein and branch chain amino acids stimulate muscle, liver and albumin synthesis and have minimal effects on tumour protein synthesis. Hence protein intake appears to favours host anabolism over tumour growth in cancer patients (53).

Our IER diet will therefore aim to maintain protein intake at 1 - 1.2 g per kg per day on restricted and unrestricted days. We anticipate the intermittent diet group will reduce energy intake by 30% overall and based on our previous data amongst patients with ABC the control group are likely to increase intake by 10% as is usually seen during treatment with chemotherapy (58). Thus overall our intervention group will have a 40% lower energy intake than our control group.

2.5 The importance of maintaining lean body mass in patients with ABC and rationale for the resistance exercise intervention

Recent data from Canada using CT scans to evaluate body compartments indicate 25% of patients with ABC (20% of the overweight and obese patients) have reduced lean body mass (sarcopenia) at the initiation of chemotherapy, and that chemotherapy toxicity and poorer outcome is specifically related to reduced lean body mass and not fat mass or BMI (52, 59). Likewise Aslani et al found reduced body nitrogen to be a key predictor of neutropenia with CMF chemotherapy amongst patients with early and ABC (60)

We have published serial measurements of body composition in an observational study of patients with MBC receiving chemotherapy (who did not receive diet or exercise advice) and reported a mean (95 % CI) loss of lean body mass of 1.9 kg (-4.9 to 1.1) during a 5 month period of chemotherapy (10). Some patients with MBC may be susceptible to loss of lean body mass which could compromise their tolerance to treatment and outcome. Since loss of lean body mass could be exacerbated when following an energy restricted diet our energy restricted intervention includes four key elements to preserve lean body mass:

1. We are using IER which appears to preferentially cause loss of fat and retain lean body mass (44). Preliminary data from the first eight women who have completed treatment with chemotherapy and IER has shown a median loss of fat 2.4 kg and gain in lean body mass of 0.7 kg (45).

2. The diet provides the recommended 1.0 - 1.2 g protein per kg per day (as outlined above).

3. The IER group will be asked to include resistance exercise three times per week. A series of recent studies demonstrate that resistance exercise is achievable, safe and can maintain or increase lean body mass and muscle function amongst patients with MBC (61-66).

4. The timing of protein intake may be important for maintaining muscle mass. It is estimated that 30g of protein is required per meal to evoke an anabolic threshold in muscle (67). We will encourage participants to spread their protein intake in three meals during the day and to include >30 g protein per main meal wherever possible on both the two restricted days and the five unrestricted days.

2.6 Rationale for investigating protein blood-based biomarkers of response to the diet and exercise interventions

Innovative mass spectrometry (MS) technologies can now be used to identify blood protein biomarkers (proteomics) that correlate with cancer patient's response to therapies. We are planning to use novel SWATH MS technology (68) to assess the proteomic plasma signature of trial participants both prior to initiation of chemotherapy and how this changes in the early stages of the diet and exercise interventions (at the start of cycle 3 or 4).

SWATH MS uses a novel technology which assesses all detectable protein components in a biological sample using a validated isobaric tagging relative quantification approach which uses 2 dimensional liquid chromatography coupled to mass spectrometry (69-72). This will allow us to assess amounts of known host proteins of interest (such as IGF-1, HIF-1 leptin, adiponectin, steroid hormones, cytokines, vascular regulators, and inflammation related molecules) as well as novel biomarkers. Novel biomarkers discovered will be validated with immunoassays (ELISA and the capillary-based NanoPro assay).

SWATH MS allows the rapid generation, in a single measurement, of a complete permanent recording of all the detectable protein components in a biological sample. SWATH maps stand as a permanent digital proteomic record, they can be interrogated over and over as novel hypotheses emerge, so samples only need to be run on the mass spectrometer once and the spectral libraries for analysis can be applied *in silico*.

We will interrogate the SWATH MS maps, comparing both baseline and dynamic changes in maps across the two treatment arms. In addition we will examine the differences in baseline maps between subsequent responders and non-responders within the diet arm. This will hopefully enable us to identify a biomarker signature predictive of both enhanced weight loss and increased chemotherapy efficacy, to be prospectively tested in future dietary intervention studies.

3. Future studies

This is a randomised phase II screening trial. (73). The design has been developed to save large numbers of patients being given an ineffective therapy, but if effective, would form the basis of a later formal phase III trial. This approach is approved by the Cancer Research UK trials organisation (CTAAC). If the results from this diet and exercise weight loss intervention are positive we will look to perform a phase III study, possibly randomising similar women to IER and resistance exercise vs metformin, if the results of the current metformin studies are also positive. A combination (IER + resistance exercise and metformin) arm will also be considered.

4. Potential risks and benefits for participating patients.

4.1 Benefits:

The intervention group will receive individual tailored advice and support to undertake an energy restricted diet and resistance exercise programme, whilst the control group will receive individual tailored advice and support to undertake a resistance exercise programme whilst continuing on their normal diet. Previous studies have reported benefits of resistance exercise in women with MBC. We consistently receive positive feedback of psychological and physical benefits from patients treated with chemotherapy participating in our diet and exercise trials. We predict that both groups will benefit from the enhanced advice and support they receive from their participation of the trial.

4.2 Risks

The additional burden and time commitment of trying to adhere to a diet and /or exercise plan during chemotherapy for ABC and potential disappointment if participants do not achieve their weight loss / exercise goal.

5. Aim

The aim of B-AHEAD 3 is to determine whether a combined IER diet and resistance exercise programme (intervention group) enhances the efficacy and ameliorates the toxicity from chemotherapy compared to the resistance exercise programme alone (control group) in women with ABC.

We will assess the effectiveness of the intervention vs control on the following outcomes:

5.1 Primary objective

Progression free survival (PFS), i.e. the time from randomisation to disease progression or death between the intervention and control group using standard RECIST criteria (Response Evaluation Criteria in Solid Tumors 1.1).

5.2 Secondary objectives

- 1. Self-reported toxicity according to the Common Terminology Criteria for Adverse Events version 4 (CTCAE v4)
- 2. Taxane neuropathy assessed with the VibraTip (McCallan Medical Ltd, Northamptonshire)
- 3. Abdominal muscle and fat cross sectional areas at the L3 level in CT scans.
- 4. Quality of life & fatigue using the FACT-B, FACT-ES (74), FACT-F (75) and FACT-BP (78) for bone pain, hospital anxiety and depression scale (76) in all patients and also: - FACT-taxane scale for patients receiving taxanes (77)
- 5. Muscle strength in the lower and upper limb. Lower limb strength from five repetition sit to stand test (FRSTST) (79). Upper limb strength assessed with hand grip dynamometry (80)
- 6. Fidelity of the interventions. Self -reported dietary intake (7 day food diary or diet history over the phone) and resistance exercise
- 7. Changes in concomitant medication
- 8. Change in blood protein biomarkers (proteomics) (Sub study 1)
- 9. Change in insulin resistance with HOMA from fasting insulin and glucose (81) (Sub study 1)
- 10. Time to Treatment Failure (TTF), i.e. the time from randomisation to disease progression, death or discontinuation of therapy due to toxicity
- 11. Objective response and clinical benefit rate (objective response plus stable disease for ≥6 months) between treatment groups
- 12. Overall survival

5.3 Exploratory objectives

1a. Is there a different proteomic signal at baseline between responders and non-responders?

1b. Is there a difference in insulin resistance at baseline between responders and non-responders?

2a. Assessment of change in PFS in women successfully losing weight (\geq 5% weight loss) vs. those who do not (<5% weight loss)

2b. Assessment of change in PFS in those with significant reductions in HOMA score vs those with no reductions.

2c. Are there differences in the change in proteomic signature between responders and non-responders?

6. Methodology

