Once the proforma has been received, the B-AHEAD 3 research team at MFT will then contact the patient to arrange a baseline appointment. The baseline appointment should ideally occur at least 2 days before commencing the planned course of chemotherapy. However potential participants will be informed that they can join the study at any time up to Day 15 of their chemotherapy cycle.

Using the initial approach we have successfully recruited 47 - 48% of eligible chemotherapy patients from the Greater Manchester NIHR Clinical Research Network into our previous randomised diet and

exercise B-AHEAD 1 and B-AHEAD 2 studies in the same hospitals outlined above. Assuming a conservative 35% uptake amongst advanced breast cancer patients we anticipate recruitment should be completed within 15 months.

Ideally baseline assessments will take place at The Nightingale Centre. It is recognised that between consent and undergoing the baseline assessments at The Nightingale Centre, participants have time to change their mind about joining the study so we are not concerned that not having this consent visit would make women join the study before they have had time to consider it.

As recruitment has been slower than anticipated, participants can now have their baseline assessments and blood samples in their recruiting hospital. Blood samples will only be taken if the centre has -80°C storage facilities or if the samples can be transferred to MFT or another centre with -80°C storage facilities within an acceptable time frame.

If baseline assessments are taking place at the recruiting hospital, there must be at least 24 hours between the participant receiving the PIS and the assessments taking place in order to allow the participant time to consider the study.

Posters and leaflets to raise awareness of the study will be displayed in patient areas.

6.4 **Procedures for during and end of the study**

The energy restriction and exercise interventions will continue until the first disease progression after commencement of study chemotherapy, even if chemotherapy had been stopped due to toxicity. Approximately 30% of patients have an objective response, whilst 20% have stable disease. The average chemotherapy period of treatment is projected to be 5.4 months. The longest treatment period is predicted to be two years. We plan to censor patients in the study once the final recruited patient has been in the trial for 12 months.

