7.3.3 Monitoring weight

All patients will have their weight monitored at each chemotherapy cycle in their chemotherapy unit. This will allow us to make any necessary modifications to their dietary prescription if patients are losing too much weight (see section 16.1 'Acting on low weight and BMI'). A change in weight by - 10% alongside a grade ≥ 2 toxicity (as per section 6.4) will be communicated to the patient's medical oncologist so they can consider whether they wish to adjust the chemotherapy dose, which are dosed according to body weight and body surface area (see section 6.4 'Procedures for during and end of the study'). Patients in Group 1 will be provided with a diary to record their weight and waist.

7.3.4 Monitoring after discontinuation of chemotherapy due to excess toxicity or at the end of planned treatment

Participants will be offered three options at this point as they will no longer be having visits to their chemotherapy hospital at each cycle:

- 1. Continue with B AHEAD 3 phone calls from the research dietitian/ physiotherapist and attend for study assessments at chemotherapy centre around every 8-12 weeks (these appointments will hopefully coincide with visits to the centre for CT scans or clinic appointments)
- Don't attend for any more study assessments with research nurses, but continue with phone calls from B-AHEAD 3 research dietitian/ physiotherapist until CT scans show tumour progression
- 3. Don't attend for any more study assessments with research nurses, no more phone calls from B-AHEAD 3 study team CT scans will continue to be monitored until tumour progression

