7.3.5 Procedure for progression of bone metastases

In the case of progression of bone metastases that stop all safe resistance exercises in view of study team, participants will be advised to discontinue the study exercises. Group 1 participants will be advised to continue with the diet and all regular review calls from study dietitian and study assessments at each cycle. Group 2 participants will no longer have review calls (unless the participant would like them to continue) as no study interventions (diet, exercise) will require review but study assessments at each cycle will continue.

7.4 **Procedure for patients leaving the trial**

Patients will leave the study at their request, or at the point that they experience disease progression (either during treatment, or after discontinuation of chemotherapy due to excess toxicity). We will ensure that there is excellent communication between oncology teams, research nurses and the B-AHEAD 3 research team to ensure patients who are progressing and leaving the study are not contacted for diet or exercise review or sent mailings by the B-AHEAD 3 team. We will however offer participants in both groups moving on diet and exercise advice from the trial dietitian and physiotherapist when they leave the study if they wish. Patients who were in the exercise only control group will not be offered information on the intermittent diet as this is our test diet and we do not have enough evidence that it is beneficial, which is the aim of the study. Patients who are still on chemotherapy at study closure will be encouraged to continue with their current regimen and be provided with "a moving forward on your own" booklet with information to help them maintain their current regimen. They will be informed that they can ring the trial dietitians if they experience any problems following the diet and exercise plans at any point in the next 12 months.

At the end of the trial we will ask the control group whether they had followed any particular diet during their chemotherapy treatment.

The participant is invited to contact the research team if they would like to receive a copy of the results, due in 2022.

Participants will be asked by their research nurse for their verbal consent for the study team to continue to review their medical records and CT scans after they leave the study.

8. Outcome measures

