10.1 Sample size and power calculations

The sample size was calculated for a phase II screening design, based on a primary outcome of progression free survival, with a time-to-event hazard ratio of 0.65, and with 90% power and a one-sided significance of 20%. Assuming that the estimated PFS in the control arm is 5.4 months, and that we will have a 15 month accrual period and a 15 month follow-up, then a total of 98 events will be required overall. This corresponds to 114 patients required in all, allowing for a 15% drop out we will need to recruit 134 patients overall. The sample size is for a randomised phase II screening design where a randomised phase III is planned in the future. This approach is approved by the Cancer Research UK trials organisation (CTAAC) (73).

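### Exploratory objective 2a compares PFS from randomisation by weight loss reached later, with no assessment time, and so favours the women who lose weight

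*Protocol*

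**What the plan says.** Section 5.3 lists objective 2a as "Assessment of change in PFS in women successfully losing weight", with the groups cut as "5% weight loss) vs. those who do not (<5% weight loss". The same wording returns in the exploratory list at the end of section 8.1. Neither place names a visit, a window or a landmark at which weight loss is judged.

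The only definition of PFS is in section 5.1: "the time from randomisation to disease progression or death between the intervention and control group". On weight, section 7.3.3 says "All patients will have their weight monitored at each chemotherapy cycle in their chemotherapy unit". Section 6.4 says "The energy restriction and exercise interventions will continue until the first disease progression after commencement of study chemotherapy", and section 7.4 adds "Patients will leave the study at their request, or at the point that they experience disease progression".

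Objective 2b is "Assessment of change in PFS in those with significant reductions in HOMA score vs those with no reductions". Sections 8.1.2 and 8.1.3 place the repeat HOMA samples around cycle 3 or 4, in the sub-study 1 subset only.

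Section 10.2 gives a Cox model for PFS between the two randomised groups. It describes no method for 2a or 2b.

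**The concern.** The grouping in 2a is a result that arises after the PFS clock has started, and it can be acquired only while a woman is still progression-free and in the study. A woman who progresses in month 2 has had little chance to lose 5% and will usually be placed in the lower group. A woman placed in the upper group has, by that fact, survived progression-free until she got there. Counting that waiting time as her PFS credits weight loss with time that it did not produce.

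The protocol's hypothesis is that weight loss and energy restriction extend PFS (section 2.2). An artefact in the same direction, and possibly as large as the effect the trial is sized to find, could not be told apart from that hypothesis.

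**Working it through.** **The protocol's own figures.** It gives no number for 2a, so the design figures serve as the yardstick. From section 10.1: hazard ratio 0.65, 90% power, one-sided 20%.

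- Events = 4 × (0.8416 + 1.2816)² / (ln 0.65)² = 4 × 4.508 / 0.1856 = 97.2, rounded up to the stated 98.
- Recruitment = 114 / 0.85 = 134.1, stated as 134.

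**Inputs for the check.**

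- From the protocol: 134 women; PFS 5.4 months, taken as an exponential median; PFS from randomisation; censoring 12 months after the last recruit with 15 months of accrual, so 12 to 27 months per woman; CT about every 9 to 12 weeks (section 8.1.1).
- Assumed, because the protocol gives neither: half of women would reach 5% if followed long enough; the time to reach it is gamma with shape 4 and mean *m* months, unrelated to PFS. The true hazard ratio is therefore 1.00.

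**Step 1: how many women are misplaced.** The hazard is λ = ln 2 / 5.4 = 0.1284 per month. The chance that a would-be weight loser is still progression-free when she reaches 5% is (1 + λm/4)⁻⁴.

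- m = 2: 1.0642⁻⁴ = 0.78, so 22% progress first
- m = 3: 1.0963⁻⁴ = 0.69, so 31% progress first
- m = 5: 1.1605⁻⁴ = 0.55, so 45% progress first

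Those women go into the lower group because they progressed early.

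**Step 2: the hazard ratio this produces.** Simulated trials were analysed with a Cox model in which ever reaching 5% before progression or censoring is treated as a baseline group.

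| Mean time to 5% | Naive HR, progression detected continuously | Naive HR, scans every 9 to 12 weeks |
|---|---|---|
| 2 months | 0.65 | about 0.8-0.9 |
| 3 months | 0.56 | about 0.65-0.76 |
| 5 months | 0.45 | about 0.50-0.59 |

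In the scan column, progression is recorded at the next scan (every 2.1 or 2.8 months). The ranges cover both intervals and small differences in how scan timing is modelled. If loss takes about 1 month on average, the naive HR with scans is 0.97-1.00.

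With continuous detection, a falsely significant benefit (two-sided 5%) appears in 64%, 88% and 98% of trials for means of 2, 3 and 5 months. With scans, the 88% falls to 58% or less.

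**Step 3: other assumptions about weight loss** (continuous detection, no true effect).

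- Loss spread evenly over months 1 to 4 in 30%, 50% or 70% of women: HR 0.66, 0.59, 0.47.
- Loss spread over months 2 to 6: HR 0.55, 0.48, 0.37.
- All loss within 0.3 to 1.0 month: HR 0.85, false benefit in 13% of trials.

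**Step 4: does the remedy work?** On null data, landmark HRs are about 0.99-1.05 and the time-dependent Cox model gives 0.97-1.05. The share lost at a 3-month landmark is 1 − 2^(−3/5.4) = 1 − 0.68 = 32%.

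**Step 5: objective 2b.** With the repeat sample assumed at 1.4 or 2.1 months (3-weekly cycles) and no true effect, analysing only re-sampled women gives HR 0.99-1.02, even with PFS counted from randomisation. Counting unsampled women as having no reduction gives about 0.62.

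**The case against.** The strongest reply is that 2a is one line in an exploratory list. The protocol sets no ever/never rule and no separate time origin for it, and a statistical analysis plan that is not shown may specify a landmark. That is fair as far as it goes: an unseen plan could cure the problem. But the protocol does fix the contrast (groups formed by a post-randomisation result) and the endpoint (counted from randomisation), and nothing in it prevents the direct reading.

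The second reply is that continuous detection exaggerates the bias here, because progression read from CT every 9 to 12 weeks gives women time to lose weight before an event can be recorded. This stands, and the scan column is the more realistic one. It assumes that every progression is found at a scan; deaths or clinical progression between scans would move the figures part of the way back.

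A reader might also infer more than the documents support:

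- **That the analysis will show a benefit whatever the truth.** It is biased in that direction, but early loss nearly removes the bias. Disease-driven loss can offset it: with the hazard doubled after weight loss, one scenario gave a naive HR of 0.98. Section 16.2 expects cachexia to be rare.
- **That 2b has the same flaw.** A woman without the repeat sample has no HOMA change, so she need not fall in either group. If only re-sampled women are compared, both groups share the same waiting time.
- **That 2a and 2b are the trial's dose-response evidence for phase III.** No section says so. Sections 3 and 10.1 present the trial as a randomised phase II screening design leading to phase III.

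**Conclusion.** The concern holds for 2a. As worded, it compares PFS from randomisation between groups formed during follow-up, and the comparison is biased towards a benefit of weight loss. With half of women assumed to reach 5% and no true effect, the spurious HR with 9 to 12 weekly scans runs from about 0.8-0.9 (mean 2 months) to 0.50-0.59 (mean 5 months), and is close to 1 at about 1 month. For slower loss it can match or exceed the target effect of 0.65. The direction follows from the protocol's wording when weight loss is unrelated to prognosis. The size rests on the assumed speed and frequency of loss, which the protocol does not give.

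For 2b the bias is conditional on how women without the repeat sample are handled. The randomised primary comparison, its 98 events and the sample size are untouched.

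**What to change.** **Objective 2a.** Either:

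- classify weight change at a fixed landmark (for example 12 weeks), include only women still progression-free then, and count PFS from the landmark; or
- enter 5% weight loss as a time-dependent covariate in the Cox model, using the weights already recorded at each cycle.

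Adjust for arm, and report the result as a non-randomised comparison. Either method removes the immortal time but not confounding by prognosis or adherence.

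**Objective 2b.** Restrict it to women with the repeat HOMA sample, start the PFS clock at that sample, and state that women without one are not counted as having no reduction.

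**Cost.** Wording only, with no new data. A 3-month landmark drops roughly a third of women from this exploratory analysis; the time-dependent model drops none. The latter needs a stated rule for weight after chemotherapy ends, because section 7.3.4 lets women decline further study assessments while their scans are still followed.
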